Treatments for each cohort are as follows:

Neoadjuvant cohort:

- Nivolumab administered intravenously (IV) over 30 minutes at 240 mg for 2 doses, on Day 1 and Day 15

Metastatic Monotherapy Cohorts:

- Nivolumab administered IV over 30 minutes at 240 mg every 2 weeks for a maximum of 24 months or until disease progression, unacceptable toxicity, or withdrawal of consent, whichever comes first.

Metastatic Combination Cohorts (Combinations A, B, C, and D):

- Combo Arm A: Nivolumab 3 mg/kg IV over 30 minutes every 2 weeks plus Ipilimumab 1 mg/kg IV over 30 minutes every 6 weeks for a maximum of 24 months or until disease progression, unacceptable toxicity, or withdrawal of consent, whichever comes first.
- Combo Arm B: Nivolumab 1 mg/kg IV over 30 minutes plus Ipilimumab 3 mg/kg IV over 30 minutes every 3 weeks for 4 doses followed by Nivolumab 240 mg IV over 30 minutes every 2 weeks for a maximum of 24 months or until disease progression, unacceptable toxicity, or withdrawal of consent, whichever comes first.
- Combo Arm C: Nivolumab 240 mg IV over 30 minutes plus BMS-986016 (relatlimab) 80 mg IV over 60 minutes administered every 2 weeks for a maximum of 24 month, or until disease progression, unacceptable toxicity, or withdrawal of consent, whichever comes first. As of Revised Protocol 05, enrollment will be closed in Combination C.
- Combo Arm D: Daratumumab 16 mg/kg IV administered weekly for the first 8 weeks. Starting at Week 3, nivolumab 240 mg IV over 30 minutes will be administered every 2 weeks. Nivolumab will be administered before the daratumumab infusion on study days when both study drugs are administered on the same day. Daratumumab 16 mg/kg will be administered every 2 weeks from Weeks 9-24. Starting at Week 25, nivolumab 480 mg IV flat dose over 30 minutes every 4 weeks; daratumumab 16 mg/kg every 4 weeks for a maximum of 24 months or until progression, unacceptable toxicity, or withdrawal of consent, whichever comes first. The infusion rates for the first, second, and subsequent daratumumab infusions should closely follow the specifications of the currently approved (USPI)/pharmacy reference manual. As of Revised Protocol 05, enrollment will be closed in Combination C.

Study Phase: 1/2

Research Hypothesis (A): Nivolumab, in the neoadjuvant setting, will be safe and tolerable in subjects with select virus positive and virus-negative tumors.

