Relatlimab is a fully human antibody specific for human LAG-3 that was isolated from immunized transgenic mice expressing human immunoglobulin genes. It is expressed as an IgG4 isotype antibody that includes a stabilizing hinge mutation (S228P) for attenuated Fc receptor binding in order to reduce or eliminate the possibility of antibody- or complement-mediated target cell killing. Relatlimab binds to a defined epitope on LAG-3 with high affinity (K_d , 0.25-0.5 nM) and specificity and potently blocks the interaction of LAG-3 with its ligand, MHC class II (IC₅₀, 0.7 nM). The antibody exhibits potent in vitro functional activity in reversing LAG-3-mediated inhibition of an antigen-specific murine T cell hybridoma overexpressing human LAG-3 (IC₅₀, 1 nM). In addition, Relatlimab enhances activation of human T cells in superantigen stimulation assays when added alone or in combination with nivolumab (anti-PD-1 antibody).

1.1.11 *Rationale to Support Dose/Schedule of Nivolumab Combined with Relatlimab*

Based on the available nonclinical combination data and the preliminary clinical data from study CA224-020, a combined dosing regimen of nivolumab 240 mg Q2W and BMS-986016 80 mg Q2W (Combo C) is selected for the metastatic cohort nivolumab plus BMS-986016 combination.

Overall, the safety profile of BMS-986016 in combination with nivolumab is manageable, with no MDT reached at the tested doses up to 80 mg BMS-986016 and 240 mg nivolumab (flat dose, 2qw), and with evaluation of 240 mg BMS-986016 and 240 mg nivolumab combination dose based on clinical cut-off of 29-Jun-2016.¹⁵³ Important examples of durable tumor regressions, as well as manageable immune-mediated adverse events provide evidence of immune activation in the subjects treated up to 80 mg BMS-986016/240 mg nivolumab. The clinical findings are supported by the preliminary pharmacokinetic (PK) and receptor occupancy (RO) findings. Peripheral CD8+ T-cell RO data measured at trough monotherapy BMS-986016 treatment shows a linear increase with dose: 74% RO at 20 mg, 84% RO at 80 mg, and 94% RO at 240 mg. A preliminary PK analysis indicates that BMS-986016 exposure parameters are generally proportional across the dose range evaluated (20 to 800 mg) and were not altered by combination with nivolumab.

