- Combo Arm B: Nivolumab 1 mg/kg IV over 30 minutes plus Ipilimumab 3 mg/kg IV over 30 minutes every 3 weeks for 4 doses followed by Nivolumab 240 mg IV over 30 minutes every 2 weeks for a maximum of 24 months or until disease progression, unacceptable toxicity, or withdrawal of consent, whichever comes first.
- Combo Arm C: Nivolumab 240 mg over 30 minutes every 2 weeks plus Anti-Lag3 (BMS-986016) 80 mg for a maximum of 24 months or until disease progression, unacceptable toxicity, or withdrawal of consent, whichever comes first.
- Combo Arm D: Daratumumab 16 mg/kg IV administered weekly for the first 8 weeks. Starting at Week 3, nivolumab 240 mg IV over 30 minutes will be administered every 2 weeks. Nivolumab will be administered before the daratumumab infusion on study days when both study drugs are administered on the same day. Daratumumab 16 mg/kg will be administered every 2 weeks from Weeks 9-24. Starting at Week 25, nivolumab 480 mg IV flat dose over 30 minutes every 4 weeks; daratumumab 16 mg/kg every 4 weeks for a maximum of 24 months or until progression, unacceptable toxicity, or withdrawal of consent, whichever comes first. The infusion rates for the first, second, and subsequent daratumumab infusions should closely follow the specifications of the currently approved (USPI)/pharmacy reference manual.¹⁸⁴

The tumor types for the neoadjuvant cohort and the study design schematic for the neoadjuvant cohort ([Figure 3.1-1](#)) are presented below:

- HPV positive SCCHN and HPV negative SCCHN
- Cervical, Vaginal, Vulvar carcinoma
- Merkel Cell Carcinoma

[figure not shown]
Figure 3.1-1: Study Design Schematic for the Neoadjuvant Cohort:

The diseases or tumor types for the recurrent/metastatic monotherapy cohort and the study design schematic for the recurrent/metastatic monotherapy cohort is presented in Figure 3.1-2 are presented below:

- EBV positive Gastric cancer,
- HPV positive SCCHN
- Cervical, vaginal, and vulvar carcinoma
- Merkel Cell carcinoma
- Nasopharyngeal Carcinoma (NPC)

Figure 3.1-2: Study Design Schematic for the Metastatic Monotherapy Cohort

The diseases or tumor types for the recurrent/metastatic combination therapy cohorts (Combo A, B and C) are listed below and the study design schematics for the recurrent/metastatic combination therapies A, B, and C are presented in Figure 3.1-3 and Figure 3.1-4.

- HPV positive SCCHN

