In all subjects for each tumor type, biopsy and submission of fresh tumor tissue, or submission of archived tumor tissue, is mandatory for all subjects. Subjects with accessible lesions where biopsy is deemed safe by the Investigator should undergo biopsy per protocol.

3.1.4 *Subjects in the Metastatic Combination Cohorts*

Upon approval of Revised Protocol 05, all Metastatic Combination Cohorts A, B, and D will enroll patients concurrently, and enrollment in Cohorts C will be closed.

Subjects with SCCHN, MCC or NPC enrolled in Combo A will be treated with nivolumab 3mg/kg every 2 weeks plus ipilimumab 1mg/kg every 6 weeks (Combo A) for a maximum of 24 months or until disease progression, unacceptable toxicity, or withdrawal of consent, whichever comes first.

Subjects with cervical cancer and anogenital HPV associated tumors (vulvar/vaginal/anal canal/penile) will be randomized (1:1) to treatment with either Combo A - nivolumab 3mg/kg every 2 weeks plus ipilimumab 1mg/kg every 6 weeks or Combo B - nivolumab 1mg/kg plus ipilimumab 3mg/kg every 3 weeks for 4 doses followed by nivolumab 240 mg every 2 weeks for a maximum of 24 months, or until disease progression, unacceptable toxicity, or withdrawal of consent, whichever comes first. With Revised Protocol 06, no new subjects will be randomized in the anogenital HPV associated tumors cohorts.

Subjects with HPV+ SCCHN with prior PD-1/PD-L1 treatment who are enrolled in Metastatic Combination Cohort (Combo C) will be treated with BMS-986016 (relatlimab) 80 mg plus nivolumab 240 mg q2w for a maximum of 24 months until disease progression, unacceptable toxicity, or withdrawal of consent, whichever comes first.

Subjects with HPV negative, positive, or unknown SCCHN who are I-O naive will be enrolled into the metastatic SCCHN Combo D (nivolumab plus daratumumab).

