4.5 Selection and Timing of Dose for Each Subject**Table 4.5-1: Study Drug Dosing**

| Cohort | Drug | Dose | Frequency of administration | Route of administration | Duration |
|---|-------------------------|------------------|-------------------------------|--|---|
| Neoadjuvant | Nivolumab | 240 mg flat dose | Day 1, Day 15 | 30 minute Intravenous (IV) infusion | Two doses |
| Metastatic Monotherapy | Nivolumab | 240 mg flat dose | every 2 weeks | 30 minute Intravenous (IV) infusion | Maximum of 24 months or until disease progression, unacceptable toxicity, or withdrawal of consent, whichever comes first |
| Neoadjuvant Subjects Treated with Study Drug Post-Standard of Care | Nivolumab | 240 mg flat dose | every 2 weeks | 30 minute Intravenous (IV) infusion | Maximum of 24 months or until disease progression, unacceptable toxicity, or withdrawal of consent, whichever comes first |
| Metastatic Combination Cohort Combo A | Nivolumab | 3 mg/kg | every 2 weeks | 30 minute Intravenous (IV) infusion | Maximum of 24 months or until disease progression, unacceptable toxicity, or withdrawal of consent, whichever comes first |
| | Ipilimumab | 1 mg/kg | every 6 weeks | 30 minute Intravenous (IV) infusion | |
| Metastatic Combination Cohort Combo B (Cervical cancer and anogenital HPV associated tumors only) | Nivolumab | 1 mg/kg | every 3 weeks for 4 doses | 30 minute Intravenous (IV) infusion | Maximum of 24 months or until disease progression, unacceptable toxicity, or withdrawal of consent, whichever comes first |
| | | 240 mg flat dose | then every 2 weeks | | |
| | Ipilimumab | 3 mg/kg | every 3 weeks for 4 doses | 30 minute Intravenous (IV) infusion | |
| Metastatic Combination Cohort Combo C | Nivolumab | 240 mg flat dose | every 4 weeks (every 2 weeks) | 30 minute Intravenous (IV) infusion | Maximum of 24 months or until disease progression, unacceptable toxicity, or withdrawal of |
| | BMS-986016 (relatlimab) | (80 mg) | (every 2 weeks) | 60 minute Intravenous (IV) infusion | |

Table 4.5-1: Study Drug Dosing

| Cohort | Drug | Dose | Frequency of administration | Route of administration | Duration |
|--|-------------|---|--|--|---|
| | | | | | consent, whichever comes first discontinuation from study |

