| Metastatic Combination Cohort Combo D | Nivolumab | 240 mg flat dose | Every 2 weeks starting at Week 3 | 30 minute Intravenous (IV) infusion | Maximum of 24 months or until disease progression, unacceptable toxicity, or withdrawal of consent, whichever comes first |
| | | 480 mg flat dose | then every 4 weeks starting at Week 25 | | |
| | | Nivolumab will be administered before daratumumab when both study drugs are administered on the same day. | | | |
| | Daratumumab | 16 mg/kg | Every week (Wks 1-8) then every 2 weeks (Wks 9-24), then every 4 weeks starting at Week 25 | Intravenous (IV) infusion See Section 4.3 | |

Neoadjuvant Cohort subjects will receive two doses of nivolumab administered at 240 mg IV on Day 1 and on Day 15 (+1 week). A delay of the 2nd dose of nivolumab is acceptable for up to 1 week (up to Day 22); however, the 2nd dose of nivolumab should not be administered after Day 22 in order to avoid postponing surgery/biopsy beyond Day 29 and subsequent standard of care.

Metastatic Monotherapy Cohort subjects will receive treatment with nivolumab on Day 1 of a treatment cycle every 2 weeks (14 days).

Metastatic Combination Cohort subjects will be assigned to receive one of the following dosing schema (starting Day 1) based on tumor type and randomization:

- Combo A: nivolumab 3 mg/kg q2 weeks + ipilimumab 1 mg/kg q6 weeks: \pm 1 week (no less than 5 weeks between doses)
- Combo B: nivolumab 1 mg/kg + ipilimumab 3 mg/kg, q3 weeks x4, followed by nivolumab 240 mg q2 weeks: +/-3 days (no less than 18 days between doses)
- Combo C: nivolumab 240 mg + BMS-986016 160 mg, q4 weeks: \pm 2 days.
- Combo D: daratumumab q1 week x8, q2 weeks (Weeks 9-24); q4 weeks starting at Week 25 + nivolumab 240 mg q2 weeks (starting at Week 3); 480 mg q4 weeks starting at Week 25. Nivolumab will be administered before daratumumab on study days when both drugs are administered on the same day. Dosing windows for daratumumab are as follows:

Weeks 1-8: -1 and +3 days; Weeks 9-24: \pm 1 week; Week 25+: up to 14 days delayed. For nivolumab, no less than 12 days between dosing is allowed.

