Subjects who complete the neoadjuvant portion of the study and complete standard of care treatment post-surgery/biopsy who develop unresectable recurrent or metastatic disease within 1 year of surgical resection, or completion of standard of care (whichever is later), may receive treatment with nivolumab monotherapy, if eligible. Eligibility assessments are detailed in [Table 5.1-5](#).

Please refer to the Pharmacy Manual for more detail. There are no pre-medications recommended on the first cycle, **except for Combo D**. All subjects in Combo D will receive pre-infusion and post-infusion medication per the descriptions in [Section 4.7.7](#) of the protocol. If an acute infusion reaction is noted, subjects should be managed according to Section 4.7.7.

Dosing modifications:

There will be no dose modifications allowed for the management of toxicities of individual subjects.

Dosing window:

When nivolumab is administered alone and in combination with BMS-986016 (relatlimab), subjects may be dosed no less than 12 days between doses during Q2 week dosing. For ipilimumab (Combo A), subjects may be dosed within a \pm 1-week window and no less than 5 weeks from the previous dose. For subjects in Combo B, when nivolumab is administered in combination with ipilimumab, subjects may be dosed within a \pm 3-day window and no less than 18 days from the previous dose. A dose given more than 3 days after the intended dose date will be considered a delay, except for subjects receiving ipilimumab in Combo A. A maximum delay of 6 weeks between doses is allowed, except for subjects in the Neoadjuvant cohort.

Daratumumab will be administered at a dose of 16 mg/kg as an IV infusion every week for the 8 doses (-1 and +3 days window is allowed), every two weeks from weeks 9 to 24 (can be delayed up to 1 week) and every four weeks from weeks 25 onwards (can be delayed up to 14 days) until toxicity or disease progression.

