| Procedure | Combo A During Treatment Nivo 3mg q2w + Ipi 1 mg/kg q6w | Combo B During Treatment Nivo 1 mg/kg + Ipi 3 mg/kg q3w x 4, followed by Nivo 240 mg q2w | Combo C During Treatment Nivo 240 mg + BMS-986016 80 mg q2w | Combo D During Treatment Daratumumab q1 week/q2weeks/q4 weeks + Nivo 240 mg q2 weeks/ 480 mg every 4 wks. | Notes See note sections below for dosing windows |
|-------------------------------------|--|---|---|--|---|
| Clinical Drug Supplies | | | | | |
| Administer Study Drug (Cohort A) | X ^a | | | | First dose to be administered within 5 days of study drug assignment. Confirmation of viral status will be required prior to study drug assignment for HPV SCCHN tumor types in the metastatic cohort. Dosing Window: +/-1 week Subjects may be dosed no less than 12 days for nivolumab and 5 weeks for ipilimumab. |
| Administer Study Drug (Cohort B) | | X ^a | | | First dose to be administered within 5 days of study drug assignment. Confirmation of viral status will be required prior to study drug assignment for HPV SCCHN tumor types in the metastatic cohort. Dosing window: ± 3 days Subjects may be dosed no less than 19 days between q3week doses of nivolumab and ipilimumab, and no less than 12 days for nivolumab monotherapy after completion of ipilimumab induction. |

Table 5.1-3: On-Treatment Assessments Metastatic Combination Therapy Cohorts (CA209358)

| Procedure | Combo A During Treatment Nivo 3mg q2w + Ipi 1 mg/kg q6w | Combo B During Treatment Nivo 1 mg/kg + Ipi 3 mg/kg q3w x 4, followed by Nivo 240 mg q2w | Combo C During Treatment Nivo 240 mg + BMS-986016 80 mg q2w | Combo D During Treatment Daratumumab q1 week/q2weeks/q4 weeks + Nivo 240 mg q2 weeks/ 480 mg every 4 wks. | Notes See note sections below for dosing windows |
|-------------------------------------|--|---|---|--|---|
| Administer Study Drug (Cohort C) | | | X | | 
First dose to be administered within 5 days of study drug assignment.
 
Confirmation of viral status will be required prior to study drug assignment for HPV SCCHN tumor types in the metastatic cohort.
 
Dosing window +/- 2 days.
 
Subjects may be dosed no less than 12 days for nivolumab and BMS-986016.
 |

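### The Combo C dosing line in Protocol 4.5 matches no other regimen in the plan and, read literally, halves weekly nivolumab; it should be corrected, but the impact is low

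*Protocol*

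**What the plan says.** Four descriptions of Combo C sit in the current text.

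- **Assigned regimen, 240/80 every 2 weeks.** The Synopsis gives "Combo Arm C: Nivolumab 240 mg IV over 30 minutes plus BMS-986016 (relatlimab) 80 mg IV over 60 minutes administered every 2 weeks". The dose rationale in Protocol 1.1.11 says "a combined dosing regimen of nivolumab 240 mg Q2W and BMS-986016 80 mg Q2W (Combo C) is selected", and Protocol 3.1.4 says subjects "will be treated with BMS-986016 (relatlimab) 80 mg plus nivolumab 240 mg q2w". The Synopsis dosing table, the header of Table 5.1-3 and SAP Table 7.4.1-1 agree. Protocol 3.1 has "Combo Arm C: Nivolumab 240 mg over 30 minutes every 2 weeks plus Anti-Lag3 (BMS-986016) 80 mg", which agrees on both doses and on the nivolumab interval but gives no relatlimab interval.
- **The 4.5 line.** "Combo C: nivolumab 240 mg + BMS-986016 160 mg, q4 weeks", with a window of plus or minus 2 days.
- **Table 4.5-1, in the same section.** The nivolumab frequency cell for Combo C begins "every 4 weeks (every 2 weeks" and then closes its parenthesis. The relatlimab cells give 80 mg and every 2 weeks, both in parentheses.
- **SAP 2.2 and 6.2.** The headline regimen is nivolumab 480 mg plus relatlimab 160 mg every 4 weeks. A rider keeps subjects enrolled before Revised Protocol 05 and treated with 240/80 every 2 weeks on that regimen.

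The dosing-window text of 4.5 assumes a 2-week interval: "in combination with BMS-986016 (relatlimab), subjects may be dosed no less than 12 days between doses during Q2 week dosing". The Cohort C row of Table 5.1-3 pairs a window of plus or minus 2 days with "Subjects may be dosed no less than 12 days for nivolumab and BMS-986016".

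**The concern.** The line is continuous prose in current protocol text, so it is neither a broken table nor a superseded entry in a change log. It stands in the section a site would consult for dose and timing, and it contradicts the window text of the same section. A site that followed it would give half the intended weekly nivolumab and twice the intended relatlimab per infusion.

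There is also a reporting risk. The SAP headline describes a regimen that, on the documents' own account, appears to have no subjects. If that sentence passed into the study report, it would misdescribe what Combo C received.

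**Working it through.** **Inputs.** Doses and intervals are those set out above. The reference for relative dose intensity is the Combo C formula in SAP Table 7.4.1-1; the reference for delay is the 14-day interval in SAP Table 7.4.2.1-1.

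**The plan's own figure.** In its Combo D note, SAP Table 7.4.1-1 gives an intended 120 mg of nivolumab a week for nominal 240 mg or 480 mg doses. This reproduces: 240/2 = 120 and 480/4 = 120. The Combo C denominator gives the same rate: (240/14) × 7 = 120.

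**Weekly dose = dose per infusion / interval in weeks.**

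| Regimen | Nivolumab, mg/week | Relatlimab, mg/week |
|---|---|---|
| Assigned, 240/80 every 2 weeks | 240/2 = 120 | 80/2 = 40 |
| SAP headline, 480/160 every 4 weeks | 480/4 = 120 | 160/4 = 40 |
| Protocol 4.5 line, 240/160 every 4 weeks | 240/4 = 60 | 160/4 = 40 |

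Over 24 weeks, nivolumab totals 6 × 240 = 1,440 mg under the line, against 12 × 240 = 2,880 mg as assigned. Relatlimab totals 960 mg either way (6 × 160 or 12 × 80).

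**Which interval fits the rest of the protocol.** Every 2 weeks, plus or minus 2 days, gives 12 to 16 days, so the minimum is exactly the 12 days in the 4.5 window text and in Table 5.1-3. Every 4 weeks, plus or minus 2 days, would give 26 to 30 days. In Table 5.5-6, footnotes c and d still refer to a 4-weekly regimen. However, the last sampling row equates 8 cycles with 16 weeks, which holds only for 2-week cycles (8 × 2 = 16, whereas 8 × 4 = 32).

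**How such dosing would show in the planned output.** For six nivolumab doses of 240 mg every 28 days, the SAP formula gives 6 × 240 / [(5 × 28 + 14) × 240/14] = 1,440/2,640 = 54.5%. Each cycle would show a delay of 28 − 14 = 14 days. Dosing by the line would therefore be visible in summaries already planned.

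**The case against.** The strongest reply is that this is an editing remnant which probably governed nobody's treatment. Much of that stands.

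- Drug vials are assigned through the interactive response system (Protocol 4.4), and 4.5 refers sites to the Pharmacy Manual. Neither is available here, but both stand between this line and an infusion. The 4.5 window text and Table 5.1-3 also point to 2-week dosing.
- Combo C closed at Revised Protocol 05. Appendix 5 says enrolment had been low and that enrolled subjects continue as planned.
- The SAP is dated 7 September 2021. With a 24-month limit, a subject still on treatment then would have started after 7 September 2019, more than 16 months after Revised Protocol 05 was issued on 18 April 2018. Correcting 4.5 now mainly corrects the record.
- The relatlimab cells of Table 4.5-1 are in parentheses, so they are not clean evidence for the 2-week regimen and need correction too.
- The check on dosing records needs no new output: SAP 7.4.1 already plans a by-subject listing.

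A reader might infer that Combo C subjects were underdosed. The documents do not support that. They report no subject dosed at 240/160 every 4 weeks, and they do not show when the line entered the protocol: the Revised Protocol 07 change summary lists no edit to 4.5, and previous protocol versions are not supplied. Nor do they show what halving nivolumab would cost. Protocol 1.1.9 reports similar activity for nivolumab monotherapy from 1 to 10 mg/kg, without stating the interval.

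A reader might also infer a toxicity risk from 160 mg of relatlimab. Protocol 1.5 reports no maximum tolerated dose up to 160 mg relatlimab with 240 mg nivolumab every 2 weeks, which is more intensive than the 4.5 line.

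What the reply does not remove is the contradiction itself. Section 4.5 states a Combo C dose that is wrong against every other statement of the regimen.

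**Conclusion.** The 4.5 line is wrong as written, and the impact is low. Followed literally, it gives 60 instead of 120 mg of nivolumab a week (−50%) and 160 instead of 80 mg of relatlimab per infusion, with weekly relatlimab unchanged at 40 mg.

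The conclusion rests on taking 240/80 every 2 weeks as the assigned regimen. The dose rationale, the treatment descriptions, the visit schedule and the SAP exposure table support that. An incomplete edit of a 480/160 regimen is a plausible cause, but that is an inference. That nobody received 4-weekly dosing is also an inference, from the enrolment closure and the SAP rider, which is why the listing should be checked before the SAP headline is removed.

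Response rate, sample size and power do not depend on this line. It would also be a mistake to conclude that the SAP intensity and delay formulas for Combo C need changing: they use the 2-week regimen and are right for it.

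**What to change.** 1. Change the Protocol 4.5 line to: *Combo C: nivolumab 240 mg + BMS-986016 80 mg, q2 weeks: ± 2 days (no less than 12 days between doses)*.
2. Make the Combo C rows of Table 4.5-1 read 240 mg every 2 weeks for nivolumab and 80 mg every 2 weeks for relatlimab, with the 4-week entry and all parentheses removed.
3. Use the by-subject dosing listing already planned in SAP 7.4.1 to look for any 160 mg relatlimab dose or any interval near 28 days in Combo C.
4. If there is none, replace the 480/160 headline in SAP 2.2 and 6.2 with 240/80 every 2 weeks, and remove the 4-weekly cycle numbers and footnotes c and d from Table 5.5-6. If there is any, keep a description of the 4-weekly regimen and establish whether it was the assigned one.
5. Leave the SAP 2-week intensity and delay formulas as they are.

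The cost is a protocol clarification, a check of a planned listing and, if that is clean, a small SAP text change. Endpoints, analyses and sample size do not change.
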